8.6 Intervention and Interactions

Patients

This is a pragmatic pilot study where 300 patients with either mild cognitive impairment, mild dementia, or unrecognized dementia and their care partners (if available) will be approached to participate in a telehealth ACP visit with a member of the patient's primary care team. Patients without willing or available care partners are still eligible to participate in the study. A list of eligible patients will be identified from the EHR using a combination of diagnosis codes and a novel risk prediction model for unrecognized dementia. The list will be provided to each corresponding site for the primary care physician to advise on the patient's capacity. Patients in which PCPs confirmed capacity will be approached first by the research team to gauge their interest in participating in the telehealth ACP visit. Patients will be asked if they have a care partner to join them in the visit. Depending on the patients' response, care partners' will be approached for participation. For patients and care partners that agree to participate, a dyad telehealth ACP visit will be scheduled. For patients who agree to participate but their care partners refused or patients who cannot identify a care partner to participate in the telehealth ACP visit, the visit will be scheduled only with the patient. Appointment information and reminders will be provided to the patient and care partner by mail, email, portal, telephone, and/or text messaging. Patients will be either be mailed (if we don't have a current email address or if patients prefer mail) or sent via email through RedCap an after-visit survey to assess patient's acceptability and appropriateness using the validated Acceptability of Intervention Measure (AIM)⁴⁰ and Intervention Appropriateness Measure (IAM)⁴⁰, and overall satisfaction with the intervention. For patients who either don't have current email address or prefer mail, a self-addressed stamped envelope will be provided for patients to mail back their survey. All patients who complete the survey will be entered into a raffle for a \$100 gift card.

Providers

Once telehealth ACP visits are completed, we will reach out up to 50 providers via email who participated in the intervention and invite them to complete a one-time RedCap survey that assesses acceptability and appropriateness using the validated Acceptability of Intervention Measure (AIM)⁴⁰ and Intervention Appropriateness Measure (IAM)⁴⁰, and overall satisfaction with the intervention. Providers will receive an email with a link to complete the survey. Completion of the survey will signify consent. If incomplete, providers will be sent a reminder email 2 weeks later to complete the survey. If still incomplete, providers will be contacted by telephone 2 weeks later. All providers who complete the survey will be entered into a raffle for a \$200 gift card.

9. SELECTION AND ENROLLMENT OF PARTICIPANTS

Patients must reside in the state of NC and have seen their primary care provider within the past 12

months. In addition, patients must have recognized or probable MCI or mild dementia AND retain the decisional capacity to complete ACP. Patients will be identified through the EHR in one of two ways: (a) diagnosis codes (ICD-10) for MCI/Dementia or (b) the EHR Risk of Alzheimer's and Dementia Assessment Rule (eRADAR⁴¹) prediction model. The use of eRADAR will help to circumvent the reality that diagnostic codes for cognitive impairment are vastly underutilized; eRADAR utilizes dementia-related symptoms and risk factors as well as healthcare utilization from the EHR to identify patients with probable unrecognized dementia (a high likelihood of dementia/cognitive impairment in the absence of diagnosis codes). The research team will send PCPs the list of eligible patients before outreach to confirm that individuals still have capacity for decision-making.

9.1 Inclusion Criteria

- 1. Age 65 years and older and residing in NC
- 2. Diagnosis of recognized or probable MCI or mild dementia
- 3. Have decisional capacity according to their PCP to complete ACP
- 4. Completed visit with their PCP within the past 12 months
- 5. Affiliated with an Accountable Care Organization.
- 6. English-speaking

9.2 Exclusion Criteria

- 1. Moderate to severe hearing loss that would preclude participating in a video or telephone intervention
- 2. No phone number available for patient.
- 3. Lives in a long-term care facility

9.3 Study Enrollment Procedures

Patients

A full waiver of consent is requested for identifying participants using the EHR algorithm. In the clinic environment, ACP is part of the standard of care. However, we are modifying this process by implementing a telehealth option to enhance documentation of the ACP visit. Therefore, we will obtain clinical consent for the telehealth visit from patients and care partners; patients and care partners are free to decline a telehealth visit for an ACP discussion.

A list of eligible patients at participating sites will be generated and will be distributed to each patient's PCP to advise on the patient's decision-making capacity.

If lack of capacity is assessed when patients are approached or after consent, we will call the patient back and use the following language: "when talking with your primary care provider, they thought actually it would be best to discuss advance care planning at your upcoming in-person visit instead of through an extra telehealth visit."

A recruitment letter/postcard will be sent to patients whose PCPs confirm capacity. The research team will approach patients via telephone for participation with a waiver of informed consent. Patients will be asked if they have a care partner/loved one to join them in the visit. Depending on the patients' response, care partners/loved ones' will be approached for participation. Upon participant agreement, a telehealth

ACP visit will be scheduled. For patients whose care partner/loved one agrees to participate, a dyad telehealth ACP visit will be scheduled. For patients who agreed to participate but care partner/loved one refuses or patients who cannot identify a care partner/loved one to participate in the telehealth ACP visit, the visit will be scheduled only with the patient. Appointment information will be sent to patients and care partners through a variety of communication channels per patient's preference (email, mailing, portal, telephone, and/or text messaging). The research staff will give a telephone call reminder and ensure understanding on how to set up the telehealth visit to the patient and care partner/loved one day before the appointment (except for Monday appointments and then the reminder call will occur the Friday prior to the appointment) in addition to sending reminders through a variety of communication channels per patient's preference (email, mailing, portal, and/or text messaging). We will document reasons for ineligibility and non-participation of eligible candidates in a study tracking log. We will also record the date of acceptance or non-acceptance for the telehealth ACP visit participation. Participants will not be compensated for participating in the telehealth ACP visit. After completion of the visit, patients will be either be mailed (if we don't have a current email address or if patients prefer mail) or sent via email through RedCap an after-visit survey to assess patient's acceptability and appropriateness using the validated Acceptability of Intervention Measure (AIM)⁴⁰ and Intervention Appropriateness Measure (IAM)⁴⁰, and overall satisfaction with the intervention. For patients who either don't have current email address or prefer USPS mail, a self-addressed, stamped envelope will be provided for patients to mail back their survey. All patients who complete the survey will be entered into a raffle for a \$100 gift card.

There are special informed consent considerations for individuals in this pragmatic study. We will seek a waiver of individual informed consent as set forth by criteria found in HHS 45 CFR 46:116:

- (i) the research involves no more than minimal risk to the subjects;
- (ii) the research could not practicably be carried out without the requested waiver or alteration;
- (iii) if the research involves using identifiable private information or identifiable biospecimens, the research could not practicably be carried out without using such information or biospecimens in an identifiable format;
- (iv) (the waiver or alteration will not adversely affect the rights and welfare of the subjects; and
- (v) whenever appropriate, the subjects or legally authorized representatives will be provided with additional pertinent information after participation.

We will also request a full HIPAA waiver of individual authorization as set forth by the following conditions:

- (1) Use or disclosure involves no more than minimal risk to the privacy of individuals because of the presence of at least the following elements:
 - An adequate plan to protect health information identifiers from improper use or disclosure,
 - An adequate plan to destroy identifiers at the earliest opportunity absent a health or research justification or legal requirement to retain them, and
 - Adequate written assurances that the PHI will not be used or disclosed to a third party except as required by law, for authorized oversight of the research study, or for other research uses and disclosures permitted by the Privacy Rule;
- (2) Research could not practicably be conducted without the waiver or alteration; and
- (3) Research could not practicably be conducted without access to and use of PHI.

To justify items 2 and 3 above, the data to be used for this study is currently and regularly collected for non-research purposes. We are seeking a waiver of informed consent from study participants and so it would not be practical to request direct HIPAA authorization. Research staff will contact study participants for clinical consent. As part of the pragmatic nature of the study, sample eligibility relies on a review of the PHI, and study outcomes will be retrieved from electronic health records as well.

Patient after-visit survey

A waiver of signed informed consent is also requested for adopters, those patients who complete the telemedicine ACP visit with a member of their primary care team since the survey poses no more than minimal risk of harm to participants and involves no procedures for which written consent is normally required outside of the research context, we are requesting a waiver of informed consent. After a patient completes their telehealth ACP visit, they will be asked to complete a one-time survey to assess acceptability and appropriateness using 2 validated surveys, the Acceptability of Intervention Measure (AIM)⁴⁰ and the Intervention Appropriateness Measure (IAM)⁴⁰, as well as overall satisfaction with the intervention. Patients will be either be mailed (if we don't have a current email address or if patients prefer mail) or sent via email through RedCap the survey. For patients who are mailed the survey, a self-addressed, stamped envelope will be provided for patients to mail back their survey. All patients who complete the survey will be entered into a raffle for a \$100 gift card.

We will seek a waiver of signed informed consent as set forth by criteria found in HHS 45 CFR 46:116: (i) the research involves no more than minimal risk to the subjects; (ii) the research could not practicably be carried out without the requested waiver or alteration; (iii) if the research involves using identifiable private information or identifiable biospecimens, the research could not practicably be carried out without using such information or biospecimens in an identifiable format; (iv) the waiver or alteration will not adversely affect the rights and welfare of the subjects; and (v) whenever appropriate, the subjects or legally authorized representatives will be provided with additional pertinent information after participation.

Providers

A waiver of signed informed consent is also requested for primary care providers facilitating the intervention. Once the telehealth ACP visits are completed, PCPs will be asked to complete a one-time REDCap survey to assess acceptability and appropriateness using 2 validated surveys, the Acceptability of Intervention Measure (AIM)⁴⁰ and the Intervention Appropriateness Measure (IAM)⁴⁰, as well as overall satisfaction with the intervention. Providers will receive an email with a link to complete the survey. Completion of the survey will signify consent. If incomplete, providers will be sent a reminder email 2 weeks later to complete the survey. If still incomplete, providers will be contacted by telephone 2 weeks later. All providers who complete the survey will be entered into a raffle for a \$200 gift card.

We will seek a waiver of signed informed consent as set forth by criteria found in HHS 45 CFR 46:116: (i) the research involves no more than minimal risk to the subjects; (ii) the research could not practicably be carried out without the requested waiver or alteration; (iii) if the research involves using identifiable private information or identifiable biospecimens, the research could not practicably be carried out without using such information or biospecimens in an identifiable format; (iv) the waiver or alteration will not adversely affect the rights and welfare of the subjects; and (v) whenever appropriate, the subjects or legally authorized representatives will be provided with additional pertinent information after participation.

10. STUDY INTERVENTIONS

10.1 Interventions, Administration, and Duration

Patients and Care Partners

A list of eligible patients at participating sites will be generated and will be distributed to each patient's PCP to advise on the patient's decision-making capacity. A recruitment postcard will be sent to patients whose PCPs confirm capacity. The research team will approach patients via telephone using a script to describe the purpose of the ACP visit and inquire about their willingness to participate. Patients will be asked if they have a care partner/loved one to join them in the visit. Depending on the patients' response, care partners/loved ones' will be approached for participation. Upon participant agreement, a telehealth ACP visit will be scheduled. For patients whose care partner/loved one agrees to participate, a dyad telehealth ACP visit will be scheduled. For patients who agreed to participate but care partner/loved ones refuse or patients who cannot identify a care partner/loved one to participate in the telehealth ACP visit, the visit will be scheduled only with the patient.

We will send the patient and care partner/loved one appointment information through a variety of communication channels per the patient's preference (email, mailing, or portal/mychart) that will include the date of the visit and what to expect during the visit. Patients and care partners will receive a telephone call to reminder them of the appointment and to ensure understanding on how to set up the telehealth visit to the patient and care partner/loved one day before the appointment (except for Monday appointments and then the reminder call will occur the Friday prior to the appointment). In addition, we will text patients a reminder message if they have phone with texting capabilities. The telehealth ACP visit will consist of a member from the patient's primary care team (physician assistant, nurse practitioner, physician) discussing ACP with the patient and if they have one, their care partner/loved one. The visit will focus on disease understanding, prognosis (if appropriate), eliciting overall healthrelated goals and values, identification of meaning in life, unacceptable care states, the role of surrogate decision-maker, and end-of-life wishes. The sites will utilize our ACPWise documentation tool to help facilitate, document, and bill for these visits. The primary care provider team will use clinical judgment to determine capacity to make clinical decisions, and if they feel the patient lacks capacity, they will rely on the patient's care partner/loved one for any clinical decisions. Participants will not be compensated for participation in the telehealth ACP visit. After a patient completes their telehealth ACP visit, they will be asked to complete a one-time survey to assess acceptability and appropriateness using 2 validated surveys, the Acceptability of Intervention Measure (AIM)⁴⁰ and the Intervention Appropriateness Measure (IAM)⁴⁰, as well as overall satisfaction with the intervention. Patients will be either be mailed (if we don't have a current email address or if patients prefer mail) or sent via email through RedCap the survey. For patients who are mailed the survey, a self-addressed, stamped envelope will be provided for patients to mail back their survey. All patients who complete the survey will be entered into a raffle for a \$100 gift card.

Providers

Once the Telehealth ACP visits are completed, we will reach out via email to all the providers who participated in the intervention and invite them to complete a one-time RedCap survey that assesses acceptability, appropriateness, and overall satisfaction with the intervention. Completion of the survey will signify consent. If incomplete, providers will be sent a reminder email 2 weeks later to complete the survey. If still incomplete, providers will be contacted by telephone 2 weeks later. All providers who complete the survey will be entered into a raffle for a \$200 gift card.

11. HANDLING OF STUDY INTERVENTION

All providers from participating sites will be trained on how to use the ACPWise documentation tool and on the study protocol.

All sites will have a manual describing visit procedure and documentation. The manual will also have a sample of the ACPWise tool and instructions for front desk personnel on how to check in a patient for a Telehealth ACP visit.

Providers that have facilitated the intervention will be asked to complete a REDCap survey and patient adopters will be asked to complete a survey to assess acceptability and appropriateness using 2 validated surveys: Acceptability of Intervention Measure (AIM) and Intervention Appropriateness Measure (IAM) along with overall satisfaction with the intervention.

12. SAFETY ASSESSMENTS

Potential risks include that some individuals may find ACP discussion to be uncomfortable, stressful, and/or depressing. This is expected to be temporary. All study staff and providers will be trained to deal with these situations and every effort will be made to address each participant's concerns or problems in the most supportive, empathic, and therapeutic manner. The potential benefits of this intervention may include overcoming barriers to ACP related to timing and travel restraints and providing patients and their care partners with an expanded opportunity to discuss their goals, values, and priorities for healthcare at the comfort of their home. We foresee that the potential benefits outweigh the potential risks of the intervention.

All study staff and/or providers will be trained to identify cues for discomfort, stress, and anxiety during the discussion of advance care planning, paying special attention to body language. Once cues have been identified, staff and/or providers will point out discomfort and ask the participant if they do not feel comfortable pursuing the discussion any longer and that they have the right to skip or end the advance care planning discussion at any time. We will make every effort to address each participant's concerns or problems in the most supportive, empathic, and therapeutic manner. If the participant wishes to skip or discontinue the advance care planning discussion, the staff and/or provider will send a message describing the event to the PI for documentation. However, we do not foresee having AEs and SAEs as this study presents no more than minimal risk of harm.

12.1 Adverse Events and Serious Adverse Events

We do not foresee having SAEs as this study presents no more than minimal risk of harm.

Definitions for adverse events (AEs) and serious adverse events (SAEs) to be used for this trial: **AE Definition:** AE is any untoward or unfavorable medical occurrence in a human study participant, including any abnormal sign of increased stress/anxiety or discomfort, temporally associated with the participants' involvement in the research, whether or not considered related to participation in the research.

AEs for this study include: Discomfort with ACP discussion, increased stress/anxiety. These events are no more than minimal risk of harm.

SAE Definition: SAEs consist of any adverse event that results in death; is life-threatening or places the participant at immediate risk of death from the event as it occurred; requires or prolongs hospitalization; causes persistent or significant disability or incapacity; results in congenital anomalies or birth defects; is another condition which investigators judge to represent significant hazards

SAEs for this pilot study include: We do not foresee having SAEs as this study presents no more than minimal risk of harm.

12.2 Reporting Procedures

Any unanticipated problems, serious and unexpected adverse events, deviations, or protocol changes will be promptly reported by the principal investigator or designated member of the research team to the IRB and sponsor or appropriate government agency if appropriate. In the case of a serious adverse event, the Wake Forest Institutional Review Board and the appropriate Program Officer at NIA IMPACT Collaboratory will be notified within 24 hours.

12.3 Safety Monitoring

The Principal Investigator (PI) will be responsible for ensuring participants' safety daily. In addition, the NIA IMPACT Collaboratory has assigned a Project Safety Officer to oversee all data and safety monitoring activities for this study. The Project Safety Officer will act in an advisory capacity to the NIA Director to monitor participant safety, evaluate the progress of the study, and review procedures for maintaining the confidentiality of data, the quality of data collection, management, and analyses. Refer to the NIA IMPACT Collaboratory Omnibus DSMB Charter for details.

13. STATISTICAL CONSIDERATIONS

13.1 Sample Size and Randomization

Two hundred individuals with either mild cognitive impairment (MCI), mild dementia, or unrecognized dementia will be approached to participate in a Telehealth ACP visit. In addition, if eligible patients have a care partner, we will approach them for participation in a dyad ACP visit (patient + care partner). In our previous randomized trial of a nurse-navigator ACP pathway (IMPACT),⁴³ 139 of 294 patients consented and completed the ACP intervention. If we assume a conservative Beta((139/10)+0.5,(155/10)+0.5) prior distribution for this rate, this presumes a prior mean rate of adoption = 47% (min=17%, 25th percentile=41%, 75th percentile = 53%, max=83%). Based on simulations, if we approach 300 eligible patients, we expect that a median of 94 participants will consent to participate and complete the telehealth intervention (25th percentile = 81, 75th percentile = 108). In >70% of our simulations, the posterior probability that the estimated intervention completion (adoption) rate is ≥40% was >0.70, thus we believe our proposed sample size will be adequate to judge whether an appropriate number of persons with unrecognized dementia or MCI will complete the ACP telehealth intervention. We do plan to oversample to have at least 20% of our population from racial/ethnic minority population. If we have issues obtaining 20%, we will try and use the area deprivation index to target at least 20% from a socioeconomic disadvantage group.

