3.3 Design

This is a pragmatic pilot study where 300 patients with recognized or probable MCI or mild dementia and their care partner (if available) will be approached to participate in a telehealth ACP visit with a member of the patient's primary care team.

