6. STUDY OBJECTIVES

6.1 Primary Objective

Evaluate the reach and adoption of a telehealth ACP intervention among patients with either mild cognitive impairment, mild dementia, or unrecognized dementia.

H1: We hypothesize that at least 50% of 300 participants (N=100) will agree to participate and at least 90% of those who agree to participate (N=80) will complete the telehealth ACP intervention.

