13.3 Data Analyses

The statistical approach for this project will be largely descriptive and focus on the estimation of key parameters for designing a subsequent embedded pragmatic clinical trial (ePCT). We've chosen to approach the primary outcomes for the pilot from a Bayesian paradigm, as it more naturally permits making probability statements concerning our criteria for adoption and the quality of ACP discussions (i.e. that at least 40% of approached patients will complete the telehealth ACP intervention, and that ≥80% of ACP discussion will be of high quality). Given that the primary endpoints are binary outcomes, we plan to use a standard conjugate Beta-Binomial hierarchical regression framework, which can accommodate covariates as needed. We expect that we will minimally evaluate variability in adoption by age, primary care practice / primary care provider, and by whether the patient was identified as having unrecognized dementia by the EHR Risk of Alzheimer's and Dementia Assessment Rule (eRADAR)⁴¹ or via diagnosis codes for MCI/ADRD.

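### Section 13.1 gives both 200 and 300 approached, its expected completers fit 200 rather than 300, and the H1 counts in 6.1 do not match their percentages

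*Combined protocol and SAP*

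**What the plan says.** Section 13.1 opens: "Two hundred individuals with either mild cognitive impairment (MCI), mild dementia, or unrecognized dementia will be approached". A few lines later it gives the simulation result for a different number: "if we approach 300 eligible patients, we expect that a median of 94 participants will consent to participate and complete the telehealth intervention". The quartiles printed beside that median are 81 and 108.

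The simulation rests on an earlier trial in which 139 of 294 patients consented and completed. That result is down-weighted to a Beta(139/10 + 0.5, 155/10 + 0.5) prior, and "this presumes a prior mean rate of adoption = 47"%, with quartiles of 41% and 53%. Adequacy is then claimed as follows: "In >70% of our simulations, the posterior probability that the estimated intervention completion (adoption) rate is ≥40% was >0.70".

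Section 3.3 states "300 patients with recognized or probable MCI or mild dementia and their care partner (if available) will be approached", and 3.5, 6.1, 8.1, 8.3 and 8.6 also use 300.

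H1 in 6.1 reads "at least 50% of 300 participants (N=100) will agree to participate and at least 90% of those who agree to participate (N=80) will complete". Section 13.3 sets the adoption criterion as "at least 40% of approached patients will complete the telehealth ACP intervention".

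**The concern.** A prior mean of 47% applied to 300 patients gives about 141 completers, yet the plan prints 94, which is 31% of 300 and below the plan's own 40% criterion. Read literally, the sample-size paragraph predicts a typical result that fails the test it then says is usually passed. H1 has a similar fault: both counts in brackets disagree with the percentages beside them.

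These figures are the sample-size justification and the counts attached to the primary hypothesis. A reader cannot tell how many patients will be approached, how many completed visits to plan for, or which H1 figures are meant. Completed visits are also the denominator of the H2 quality proportion, so its expected precision depends on which yield is right.

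**Working it through.** **Inputs.** Prior parameters from 13.1: a = 139/10 + 0.5 = 14.4 and b = 155/10 + 0.5 = 16.0. Number approached: n = 200 or 300 (both in 13.1). Criterion from 13.1: posterior P(rate ≥ 0.40) > 0.70. H1 percentages from 6.1.

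**1. The prior reproduces.** Mean a/(a + b) = 14.4/30.4 = 0.474; quartiles 0.412 and 0.535 (0.5347 before rounding). These agree with the printed 47%, 41% and 53%, so the model is correctly identified.

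**2. Expected completers.** With p ~ Beta(14.4, 16.0) and X | p ~ Binomial(n, p), X is Beta-Binomial(n, 14.4, 16.0), with mean n × 0.4737. Exact quantiles:

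| Approached | Mean | 25th | Median | 75th |
|---|---|---|---|---|
| Printed, for 300 | – | 81 | 94 | 108 |
| 300 | 142.1 | 123 | 142 | 161 |
| 200 | 94.7 | 82 | 95 | 108 |

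At n = 300, P(X ≤ 94) = 0.044 and P(X ≤ 108) = 0.118, so the printed median and 75th percentile sit near the 4th and 12th percentiles. Across values of n, only 198 to 201 match all three printed figures within one patient.

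**3. Alternative priors do not rescue 300.**
- Dropping the +0.5 gives exactly 81, 94 and 108 at n = 200, but 122, 142 and 161 at n = 300.
- The full-weight prior Beta(139.5, 155.5) and a fixed rate of 139/294 also give a median of 142 at n = 300.

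**4. Simulation error does not explain it.** The number of simulations is not given. Assuming 1,000, the 95% ranges for the simulated quartiles and median are:
- n = 200: 80–83, 93–96 and 106–109, which cover the printed values.
- n = 300: 120–125, 140–144 and 159–164, which do not.

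**5. The printed counts against the adequacy sentence.** After x completers of 300, the posterior is Beta(14.4 + x, 316.0 − x).

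| x of 300 | P(rate ≥ 0.40) |
|---|---|
| 94 | 0.003 |
| 108 | 0.13 |
| 122 | 0.680 |
| 123 | 0.719 |

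The criterion thus needs at least 123 completers (125 with a flat or Jeffreys prior). If the 75th percentile were 108, at most about 25% of simulations would exceed 108, so more than 70% could not reach 123.

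**6. The adequacy sentence by itself.** Probability of meeting the criterion:

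| Approached | Stated prior (needed count) | Flat or Jeffreys prior (needed count) |
|---|---|---|
| 300 | 75.2% (123) | 72.9% (125) |
| 200 | 75.0% (82) | 71.6% (84) |

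The claim of more than 70% holds in every case.

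**7. H1 counts.**

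| Quantity | At 300 | At 200 | Printed in 6.1 |
|---|---|---|---|
| 50% agree | 150 | 100 | 100 |
| 90% of those complete | 135 | 90 | 80 |
| 40% of approached (13.3) | 120 | 80 | – |

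The 100 fits 200 approached. The 80 is not 90% of those agreeing at either size. It does equal 40% of 200, but the documents do not say that it came from there.

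**8. Effect on H2.** With a quality proportion of 80% and a normal approximation, the 95% half-width is 1.96 × √(0.8 × 0.2/94) = 0.081 with 94 visits and 1.96 × √(0.8 × 0.2/142) = 0.066 with 142.

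**The case against.** The strongest reply is that nothing decided in the trial turns on these counts. The study is a largely descriptive pilot. Reach, adoption and the 40% and 80% criteria are proportions, and no stopping rule or analysis takes 94, 100 or 80 as an input. The intended size is hardly in doubt, since only the opening of 13.1 says two hundred. The corrected yield is better than the printed one, so the plan undersells itself. The H2 half-width is also a reviewer's measure: the plan states no target precision there and intends a Bayesian analysis.

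Most of this stands as far as it goes. The sample is not shown to be inadequate, no passage makes 80 completers a target, and the precision difference is modest (8.1 against 6.6 points) and favours 300. It is also fair that the link to 200 is inferred from the match, because the simulation code is not in the documents.

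It does not remove the error. The sample-size paragraph names two sizes, and two of its sentences cannot both be true at 300. The primary hypothesis carries two wrong counts, and changing the denominator repairs only one of them. A pilot meant to supply planning figures for a later trial should state its own expected yield correctly.

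**Conclusion.** The point holds and must be fixed. Section 13.1 states two numbers approached, and its completer figures of 94 (81, 108) are consistent with about 200 approached, not the 300 to which they are attached. At 300 the stated prior gives 142 (123, 161), so the printed median is about 48 too low. In 6.1 the count for 50% of 300 should be 150, and the 80 is incompatible with 90% at either size.

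The conclusion that the sample is adequate is not overturned: roughly 75% of simulations meet the criterion at 200 or 300, and 72% to 73% with a flat or Jeffreys analysis prior. The result assumes that the simulation drew the adoption rate from the stated prior and completers from a binomial, which the reproduced prior summaries support. The prior variants tried leave the median at 300 unchanged.

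**What to change.** State one number approached throughout.

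**If 300**, as every other section has it:
- In 13.1, change the opening number to three hundred.
- Rerun the simulation at n = 300 and report its quartiles and median. The exact values to check against are 123, 142 and 161; simulated values may differ by a few patients.
- Confirm that the claim of more than 70% was run at 300 (recomputed at about 75%).
- In 6.1, change the first count to 150.
- Reconcile the 90% and the count of 80 with each other and with the 13.3 criterion: 90% of 150 is 135, and 40% of 300 is 120. The sponsor must say whether the percentage or the count was meant.

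**If 200**:
- Correct 300 in 3.3, 3.5, 6.1, 8.1, 8.3, 8.6 and the simulation sentence of 13.1.
- Reconcile the 80 with the 90% in the same way: 90% of 100 is 90, and 40% of 200 is 80.

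The cost is wording in 13.1 and 6.1 and one simulation rerun, plus five further sections (3.3, 3.5, 8.1, 8.3 and 8.6) if 200 was intended. The design does not change.
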